### **Special Precautions:**

- All study material will be coded to de-identify participants and a separate list will be kept with the participant's ID and name.

**Confidentiality:**

- The study investigators, along with the IRB, will have access to the individual participant's results. Neither names nor personal information will be recorded or included in the data analysis. The investigators will strictly adhere to IRB guidelines to ensure that participant's confidentiality is maintained.

**Plans for Data Analysis:**

- The data collected will include swallow frequency (calculated as swallows per minute), peak effort amplitude (the highest amplitude of swallowing effort), and swallowing speed (the difference between the onset and offset of muscle contraction). Simple 1-way repeated measures ANOVA will be used to determine significant differences in swallowing frequency between oxygen flow rates ( $p < .05$ ). A 4-way mixed methods repeated measures ANOVA (HFNC x volume x viscosity x age) will be used to determine significant differences in amplitude and timing ( $p < .05$ ).

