## Specific Aims

The primary aim of this research is to determine the impact of different flow rates of a high-flow nasal cannula on spontaneous swallowing frequency at rest and swallowing effort and timing while swallowing.

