## **Experimental Design and methods**

This is a prospective study designed to measure swallowing frequency and swallowing effort in fifty healthy adult volunteers (25 participants will be between 21 and 49 years old; and the other 25 above 50 years old). To recruit volunteer participants, an email will be sent via university internal email system to the faculty, students and employees in the departments of Respiratory Care and Speech Language Pathology. Snowball sampling (non-probability sampling) will also be utilized to recruit individuals outside of those departments. No compensation is offered to the participants. Enrolled participants are sub-categorized into two different age groups to

determine if there are any swallowing differences between the different age groups. Inclusion criteria include individuals who are older than 21 years of age and have no cognitive impairment. Exclusion criteria include individuals who are less than 21 years of age, have a history of dysphagia or disease/condition that may cause dysphagia, current use of medications that alter swallowing function, nasal obstruction, and the presence of a tracheostomy tube.

Upon meeting inclusion criteria, informed consent explaining the procedure and potential harm will be obtained and a copy will be given to the subject. Then, a unique identification code number will be assigned to protect the subject's identity.

HFNC:

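### Swallowing frequency is tested by flow rate only, so the age comparison behind the 25/25 enrolment is never made for this outcome

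*Combined protocol and SAP*

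**What the plan says.** The Specific Aims section asks about "the impact of different flow rates of a high-flow nasal cannula on spontaneous swallowing frequency at rest", and about swallowing effort and timing. Age is not part of the aim.

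Experimental Design and methods describes a study "designed to measure swallowing frequency and swallowing effort in fifty healthy adult volunteers". It fixes the split: "25 participants will be between 21 and 49 years old; and the other 25 above 50 years old". It then gives the reason for the split: "Enrolled participants are sub-categorized into two different age groups to" "determine if there are any swallowing differences between the different age groups". That purpose is not restricted to any one outcome.

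Plans for Data Analysis lists three outcomes: frequency, peak amplitude and swallowing speed (timing). For frequency: "Simple 1-way repeated measures ANOVA will be used to determine significant differences in swallowing frequency between oxygen flow rates". For the other two: "A 4-way mixed methods repeated measures ANOVA (HFNC x volume x viscosity x age) will be used". No other section plans an age analysis of frequency.

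**The concern.** The design section sets up a between-person age comparison in a study of frequency and effort, and the analysis section carries it out for effort and timing only. In a 1-way repeated-measures ANOVA on flow, differences in people's overall level, age included, go into the subject term. Any difference between age groups in their response to flow goes into the error term. The age question for frequency is therefore absent from the plan, not merely underpowered.

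Followed as written, the plan leaves a stated reason for the enrolment unanswered for one of three outcomes. Readers would also see only an average flow effect, with no indication of whether it describes both age groups. If the age analysis were added after the data were seen, it would be post hoc. Opposite responses in the two groups could also mask each other in the average, but this is hypothetical: the documents do not predict it, and cancellation is complete only if the responses are equal and opposite.

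**Working it through.** **What the documents supply.** N = 50, as 25 + 25 by age (Experimental Design and methods). Frequency is recorded on room air and at three flows (Swallowing Frequency), so there are k = 4 levels, or k = 3 if room air is left out of the ANOVA. Alpha is 0.05 (Plans for Data Analysis). There is no effect size, SD, power or sample-size derivation, so the plan has no figure of its own to reproduce.

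**What each model tests (50 completers).**

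| Term | Planned 1-way | Flow × age mixed |
|---|---|---|
| Flow, k = 4 | F(3, 49×3 = 147) | F(3, 48×3 = 144) |
| Flow, k = 3 | F(2, 49×2 = 98) | F(2, 48×2 = 96) |
| Age | not tested | F(1, 48) |
| Flow × age | not tested | F(3, 144) or F(2, 96) |

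This table is the finding, and it needs no assumed values. The rest is illustration.

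**Assumptions for the illustration.** Within-person SD 1, between-person SD 1, and linear change across four levels unless stated. Simulated figures use 10,000 trials per setting.

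**Age term.**
- Noncentral t with 25 per group and 48 df gives 80% power at d = 0.809, in units of the SD of a person's mean.
- That SD is √(σ_b² + σ_w²/k): √(1 + 1/4) = 1.118 for four levels and √(1 + 1/3) = 1.155 for three. The detectable age difference is 0.809 × 1.118 = 0.904, or 0.809 × 1.155 = 0.934, within-person SD.
- 95% CI half-width: t(0.975, 48) × √(2/25) = 2.011 × 0.283 = 0.569 SD of the person-level mean.
- With an age shift of 1.0 and no flow effect, the age term rejects in 87.5% of simulated trials. The planned flow test rejects in 5.1%, its false-positive rate.
- The 87.5% depends on the variance ratio. For the same shift with four levels:

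| Between-person SD | SD of person's mean | Power for age | Difference detectable at 80% |
|---|---|---|---|
| 0.5 | 0.707 | above 99% | 0.57 |
| 1 | 1.118 | 87% | 0.90 |
| 2 | 2.062 | 39% | 1.67 |
| 3 | 3.041 | 21% | 2.46 |

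**Flow term.** If both groups change by 0.8, λ = 50 × 0.8² × SS, where SS is the sum of squared centred level scores. For scores 0, 1/3, 2/3, 1, SS = 5/9 and λ = 17.8. Power is 95% in both models (simulated 94.9% and 95.0%; three levels, 95.2% in both).

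**Interaction term.** If the groups' changes differ by D, each departs from the average by D/2, so λ = 50 × (D/2)² × SS = 12.5 × D² × SS. For linear change SS = 5/9; if all the change is at one level, SS = 1 − 1/4 = 0.75.

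| Scenario | λ, linear | Power, linear (simulated) | λ, one level | Power, one level (simulated) |
|---|---|---|---|---|
| 0.8 v 0 (D = 0.8) | 4.44 | 39% (39.2%) | 6.00 | 51% (50.7%) |
| 0.8 v 0.4 (D = 0.4) | 1.11 | 12% (12.3%) | 1.50 | 15% (15.0%) |

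Eighty per cent power needs D = 1.27 (linear) or 1.09 (one level). With three levels and linear change, simulated power is 41.4% for 0.8 v 0 and 13.0% for 0.8 v 0.4.

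**The case against.** The strongest counter-reading is that age was meant for effort and timing only. The background section on swallowing effort and timing cites age as an influence on amplitude and timing; the background on spontaneous frequency does not mention age; and the sentence explaining the age groups does not name frequency. That reading is coherent, but the text does not impose it. The stated purpose covers any swallowing difference, and the same section opens by naming frequency as a measured outcome. If a restriction was intended, the plan needs to say so.

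Second, the aim concerns flow, and the planned flow test answers it. This stands, and it is why the flow effect should stay primary.

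Third, the contrast of 5% with 88% shows only that a model without an age term cannot detect age, and the 88% rests on one assumed variance ratio. This also stands: the range is 21% to above 99%. The scale-free figure of 0.81 SD is the one to rely on.

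Fourth, the interaction test is weak, so readers will often still not know whether the groups respond alike. That is true of the p-value. It argues for reporting by-age estimates with intervals and stating the limit, not for leaving the comparison out.

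Two small points also hold. The degrees of freedom assume 50 completers, although Risk to subject provides for withdrawals. The age bands leave a person aged exactly 50 without a group.

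**Conclusion.** The concern holds. The plan tests age for amplitude and timing but not for frequency, although the design section gives an unrestricted purpose for the age groups in a study that measures frequency. The flow result is not invalid and loses no meaningful power; what is missing is the age main effect and the flow-by-age interaction for one of three outcomes. That conclusion rests on the text and the model structure alone.

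What the added terms could deliver is modest: about 80% power only for a large age difference, and for interaction only when the groups' changes differ by about 1.1 to 1.3 within-person SD. The 0.81 SD figure and the CI half-width do not depend on the assumed SDs; the simulated powers do. This is a change the sponsor should make, because it answers a question the trial itself poses from data it already collects.

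**What to change.** Replace the 1-way ANOVA for frequency with a flow (within-person) × age group (between-person) mixed ANOVA or mixed model:

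- Keep the flow main effect as the primary test for frequency.
- Report the age main effect, the flow-by-age interaction, and flow estimates with 95% CIs in each age group, with the by-age estimates labelled secondary.
- State that 25 v 25 gives about 80% power only for an age difference of about 0.81 SD of the person-level mean, and that a non-significant interaction does not show that the groups respond alike.

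If the sponsor does intend the age question for amplitude and timing only, the design section should say so. That removes the mismatch but leaves frequency by age unexamined.

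The cost is about two sentences in Plans for Data Analysis and no new data, since age is an enrolment criterion (a person aged exactly 50 must be assigned to a group). Error degrees of freedom fall from 147 to 144, or from 98 to 96, and power for flow is essentially unchanged.
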